## **12. Withdrawal**

At any point during the study, a subject may withdraw from the study. The subject may refuse to take part in or stop taking part in this study at any time. The subject will be instructed to call the investigator in charge of this study if they decide to do this. Their decision not to take part in the study will not affect their current or future medical care or any benefits to which they are entitled. If they wish to withdraw, they will be provided contact details for the study team to initiate their withdrawal.

Early termination from the study is also subject to the PI's discretion. Subject will no longer be in the study and data will no longer be collected. The reasons for this withdrawal could be due to study non-compliance or if the subject no longer meets eligibility requirements. A member of the study team will notify the study participant if they will no longer be participating in the study.

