## 3.0 Intervention to be studied

Subjects will be screened for likely inclusion during the summer months. Baseline demographics, medical comorbidities, and URI symptoms will be assessed. Informed consent will be completed.

The fall URI season typically runs through September and October (Turner R et al). Towards the end of screening, all subjects will be randomized 2:1 to active use of Sinusonic (128Hz) for 1 minute 3 times daily or an identical “placebo” device that emits a frequency of 1,000 Hz and has the ball valve modified to eliminate positive expiratory pressure. Devices will be shipped to home addresses via overnight mail. On September 1, 2020 all subjects will begin daily use of their assigned device. Subjects will remain blinded as to treatment arm until study completion.

Subjects will be asked to complete a brief daily questionnaire on URI symptoms and whether or not they feel as if they have a “cold”. Previously validated questions for viral URI studies are rating 8 items on a likert scale from 0 (no symptoms) to 3 (severe symptoms) (Jackson GG, et al). The 8 symptoms are: sneezing, runny nose, nasal obstruction, sore throat, cough, headache, malaise, and chilliness. A Total Symptom Score (TSS) will be the sum of each symptom to provide a daily score ranging from 0 to 24. Prior studies have defined the common cold as present when:

- 1)  $TSS \geq 14$  PLUS moderate or severe nasal discharge x 3 days OR patient subjective impression they have a cold OR

2) TSS < 14 AND moderate or severe nasal discharge x 3 days AND subjective impression they have a cold

Answers will be uploaded to secure REDCAP database. The study duration is 8 weeks. At the end of the study, subjects will be asked questions regarding device safety and tolerability.

Our primary outcome will be absolute number of URIs experienced during the 8 week study period. Secondary outcomes will be time to first URI, duration and symptom severity of viral URIs. These metrics will allow us to determine if Sinusonic decreases the frequency of URIs, as well as potentially shortening the duration or decreasing the severity of URIs.

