## **18.0 Data safety monitoring and reporting**

Patients will initially be screened over the phone and informed consent obtained. This will occur during the summer months so we have a group of 300 subjects who pass this initial screen. Towards the end of the screening period, we will re-contact patients to confirm their interest in participation. As described above, we will also ask symptom scores to ensure TSS<9 and patient does not have an active URI at the start of the study.

If patients still wish to participate and still meet inclusion criteria, they will be randomized and devices shipped out within a week.

Safety will be monitored throughout the study based upon self reporting of symptoms. Subjects will be advised to seek medical care if at any time their symptoms become severe. Review of the daily reports will occur weekly to ensure the condition of each patient is adequately monitored for possible signs of URI or COVID19.

The period of observation for collection of non-serious adverse events extends from the time the subject gives informed consent until completion of the End-of-study visit or Early Termination Visit. Serious adverse events (SAE) will be reported from the time of informed consent through 30 days after the last use of the SinuSonic. Adverse event data listings will be reviewed at regular intervals throughout the study. In addition, investigators will be alerted of Adverse Events of interest via automated emails programmed in the EDC system. Patient compliance will be assessed via weekly phone calls from study coordinator.

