## **DAILY URI SYMPTOM SCORE**

**To be completed each evening**

PLEASE RATE HOW BOthersome YOUR SYMPTOMS  
HAVE BEEN OVER THE PAST DAY

	Not at all	Mild	Moderate	Severe
Lost sense of smell/taste	0	1	2	3
Sneezing	0	1	2	3
Runny nose or thick nasal discharge	0	1	2	3
Nasal obstruction or congestion	0	1	2	3
Sore throat	0	1	2	3
Cough	0	1	2	3
Headache	0	1	2	3
Malaise (feeling unwell or exhausted)	0	1	2	3
Chilliness	0	1	2	3
TOTAL SYMPTOM SCORE (TSS) of last 8 items				

Do you feel like you have a cold today? Yes/No

How many times did you use Sinusonic in the last 24 hours?

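### Section 12 ends outcome collection when the investigator ends a subject's participation, with non-compliance a named reason, and Section 10.0 names no all-randomised analysis and no rule for a partly observed 8-week URI count

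*Combined protocol and SAP*

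**What the plan says.** Section 12 provides that "Early termination from the study is also subject to the PI's discretion". The consequence follows: "Subject will no longer be in the study and data will no longer be collected". Possible grounds are then given: "The reasons for this withdrawal could be due to study non-compliance or if the subject no longer meets eligibility requirements". Non-compliance is not defined. It could mean not using the device, not returning diaries, or both. The data stop is attached to termination by the investigator. Section 12 does not say what happens to data collection after a subject's own withdrawal.

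Compliance is tracked on study in two ways. Section 18.0 says "Patient compliance will be assessed via weekly phone calls from study coordinator", and the daily symptom form in the Appendix asks "How many times did you use Sinusonic in the last 24 hours". No threshold is attached to either.

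The outcomes need follow-up to the end. Section 3.0 states "Our primary outcome will be absolute number of URIs experienced during the 8 week study period" and "Secondary outcomes will be time to first URI, duration and symptom severity of viral URIs".

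Section 10.0 lists software, outcomes, families of tests and a p-value threshold. It names no analysis set, missing-data method, exposure term or censoring rule. It assigns no test to the URI count and does not mention time to first URI. No other section fills these gaps. The column heading with N=300 in the Section 9.1 schedule describes who attends, not who is analysed.

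**The concern.** Device compliance can be judged only after a device has been assigned, so a subject removed for it is selected on behaviour that the assigned arm may influence. The arms differ physically: the active device gives expiratory resistance, while the sham "has the ball valve modified to eliminate positive expiratory pressure". Different tolerability or adherence is therefore plausible, although nothing in the documents shows it. Blinding of subjects does not make adherence equal.

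Two things are at stake. First, if removal is related to both arm and outcome, the lost diary time is informative, and no later analysis can recover what was not collected. Second, even removal unrelated to outcome distorts a raw count if it is more frequent in one arm, because those subjects had less time in which to record a URI. Without a stated analysis set and partial-follow-up rule, these choices could be made after the data are seen.

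**Working it through.** **Inputs from the documents.** 200 active and 100 sham subjects; URI in 50% of sham and 33% of active subjects (Section 5.0); significance at p ≤ 0.05 (Section 10.0); 8 weeks of observation (Section 3.0).

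**Assumptions, because the documents are silent.** Two-sided test; removal rates of 5%, 10% and 20%; removal at week 4; Poisson counts; one-way ANOVA on one count per subject.

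**1. The plan's own figure.** Two-proportion test with pooled variance under the null:
- Pooled proportion = (100×0.50 + 200×0.33)/300 = 0.3867.
- Null SE = √[0.3867×0.6133×(1/100 + 1/200)] = 0.0596.
- Alternative SE = √[0.50×0.50/100 + 0.33×0.67/200] = 0.0600.
- Power = Φ[(0.17 − 1.96×0.0596)/0.0600] = 81.2%.

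The plan states no power level. At 80% power the same method needs 98 + 196 = 294, so the planned 300 reproduces, with little slack and no stated dropout allowance.

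**2. Loss unrelated to outcome, equal in both arms.** Replace each n by n(1 − L). For L = 5%, 10% and 20%, power is 79.2%, 77.0% and 72.1%. Type I error stays at 5%.

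**3. Partial counts used as if complete, no true effect.** If 50% have at least one URI, the Poisson mean is −ln(0.5) = 0.693 in each arm. Removal at week 4 of a share a of the active arm and s of the sham arm, regardless of outcome, gives an expected raw count ratio of (1 − a/2)/(1 − s/2) instead of 1. Type I error is by simulation; ranges cover independent runs.

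| Removed, active vs sham | Raw count ratio | Type I error, ANOVA on raw counts |
|---|---|---|
| 5% vs 0% | 0.975 | about 5–6% |
| 10% vs 0% | 0.95 | about 6–7% |
| 20% vs 0% | 0.90 | about 11% |
| 5% vs 2.5% | 0.975/0.9875 = 0.987 | about 5% |
| 10% vs 5% | 0.95/0.975 = 0.974 | about 5–6% |
| 20% vs 10% | 0.90/0.95 = 0.947 | about 6.5% |
| equal | 1 | 5% |

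The first three rows are an upper-end case, since they assume no sham removals at all. In those rows a rate test with observed time as exposure stays at about 5%. That holds because removal here is unrelated to outcome; an exposure term alone would not repair outcome-related removal.

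**4. Removed subjects dropped altogether, active arm only, no true effect (50% vs 50%).** This adds a further assumption, as the plan does not say that removed subjects are excluded. If shares I of infected and U of uninfected active subjects are lost, the active proportion is 0.5(1 − I)/[0.5(1 − I) + 0.5(1 − U)], and the active n is 200 times that denominator.
- I = 10%, U = 5%: 0.45/0.925 = 0.486, n = 185, type I error 5.5%.
- I = 10%, U = 0: 0.45/0.95 = 0.474, n = 190, 7.1%.
- I = 20%, U = 10%: 0.40/0.85 = 0.471, n = 170, 7.5%.
- I = 20%, U = 0 (extreme): 0.40/0.90 = 0.444, n = 180, 14.5%.

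The same loss in both arms gives 5.0%.

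**The case against.** The strongest reply is that the effect may be small. Section 12 is permissive, no removal rate is given, and sham subjects carry the same device schedule and diary. With removals twice as common in the active arm, the inflation is negligible up to 10% and modest at 20%. This stands, and it limits the size of the point. It does not supply the missing rule.

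The study is also called a pilot (Section 9.0) and exploratory (Section 10.0). That lowers the stakes, but the plan still names a primary outcome, a significance threshold and a powered comparison. Nor can intention-to-treat be taken as implied: nothing says so, and an all-randomised set cannot restore diaries that were never collected.

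A reader might infer more than the documents support:
- *That a subject can be removed for catching a URI, because the low-symptom criterion is then no longer met.* Section 12 puts no time limit on eligibility, but Sections 4.0, 9.1 and 18.0 apply the no-URI and TSS<9 criteria at entry. This is a wording gap, not a stated practice.
- *That data already recorded are discarded, or that removed subjects are excluded.* Section 12 stops future collection only, and Section 10.0 is silent on exclusion.
- *That safety follow-up ends as well.* Section 11.0 provides for an early termination visit, serious adverse event reporting to 30 days after last use, and follow-up of adverse events to resolution. The two sections need reconciling, but Section 11.0 does not keep the URI diary running.

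**Conclusion.** The point holds in this form: a written rule stops primary-outcome collection for subjects whom the investigator removes, non-compliance after randomisation is a named ground, and the analysis section has neither an all-randomised set nor a rule for partial follow-up. It should be fixed.

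Its size cannot be fixed from the documents. Power loss is 2 to 9 percentage points (81% to 79%, 77% or 72%) for 5% to 20% loss in both arms. Type I error stays at 5% under equal removal, is about 5% to 6.5% under twofold imbalance, and reaches about 11% if 20% are removed from the active arm alone. The 5.5% to 14.5% range applies only if removed subjects are also dropped, and only from the active arm. All of this rests on assumed removal rates, and the count results also on assumed timing and an assumed test. A reader might infer bias in favour of the device because the illustrations place more removals in the active arm. The documents do not support that: the direction is unknown.

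**What to change.** **Section 12.** Replace the sentence that stops data collection with: *Ending a subject's participation or device use at the investigator's discretion does not by itself end outcome data collection: the daily diary and week 8 questions continue unless the subject withdraws consent to further data collection. A URI or raised TSS after study start is an outcome and is not a reason to stop collecting data. The date and reason of each removal are reported by arm.*

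This leaves untouched the grounds on which the investigator may end device use or participation. In addition:
- Define study non-compliance (device use, diary return, or both).
- State whether a URI between randomisation (Day 1 in Section 9.1) and study start (Day 12) counts as an outcome.
- Reconcile the data stop with the adverse event follow-up in Section 11.0.

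**Section 10.0.** Add: *The primary analysis includes all randomised subjects in their assigned arm, using all observed diary data, and accounts for observed diary time (for example a Poisson or negative binomial rate with a log-exposure offset). Time to first URI is censored at the last diary day. Subjects with no diary day are reported by arm, and a sensitivity analysis addresses missing diary time. An analysis of compliant subjects, with the threshold fixed before unblinding, is supportive only.* The rate model is one option; what matters is that observed time is accounted for.

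**Cost.** Wording in two sections and some continued follow-up through a diary that is already electronic. Little will be recovered from subjects removed for not returning diaries, which is why the sensitivity analysis is needed. Keeping non-compliant subjects may dilute the device effect; the supportive analysis can show by how much.

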## **13.0 Risks to Subjects**

There are risks to subjects using the SinuSonic device. Subjects may experience a degree of discomfort, nosebleeds or crusting due to use of the device. Prior studies have reported: Mild discomfort in 2.5-5% of patients; Bleeding in 0% of patients; Crusting in 0% of patients (Soler ZM et al).

There is a risk of a loss of confidentiality of your personal information as a result of participation in this study.

## **14.0 Potential Benefits to Subjects or Others**

This study is for research purposes only. Participants may benefit from decreased infections with potentially milder symptoms or shorter duration, but we do not know if this will occur. Information learned from the study may help other people in the future.

## **15.0 Sharing of Results with Subjects**

Information about the subjects (including identifiable private information) may have all of their identifiers removed and used for future research studies.

Records of the subjects' participation in this study will be held confidential except as disclosure is required by law or as described in the ICF.

## **16.0 Payment**

For participating in this study, participants will be given a free device, but no payment will be given.

## **17.0 Devices**

Dispensing and storage of SinuSonic devices will be done by the study sponsor.

## **18.0 Data safety monitoring and reporting**

Patients will initially be screened over the phone and informed consent obtained. This will occur during the summer months so we have a group of 300 subjects who pass this initial screen. Towards the end of the screening period, we will re-contact patients to confirm their interest in participation. As described above, we will also ask symptom scores to ensure TSS<9 and patient does not have an active URI at the start of the study.

If patients still wish to participate and still meet inclusion criteria, they will be randomized and devices shipped out within a week.

Safety will be monitored throughout the study based upon self reporting of symptoms. Subjects will be advised to seek medical care if at any time their symptoms become severe. Review of the daily reports will occur weekly to ensure the condition of each patient is adequately monitored for possible signs of URI or COVID19.

The period of observation for collection of non-serious adverse events extends from the time the subject gives informed consent until completion of the End-of-study visit or Early Termination Visit. Serious adverse events (SAE) will be reported from the time of informed consent through 30 days after the last use of the SinuSonic. Adverse event data listings will be reviewed at regular intervals throughout the study. In addition, investigators will be alerted of Adverse Events of interest via automated emails programmed in the EDC system. Patient compliance will be assessed via weekly phone calls from study coordinator.

## APPENDIX

### **SCREENING CRITERIA (all must be no):**

QUESTIONS	YES	NO
Have you had sinusitis, otitis or laryngitis or any other upper respiratory illness in the last 2 weeks?		
Have you used topical nasal decongestant spray in the last week?		
Do you currently have nasal crusting or history of ulcers or perforation?		
Have you had severe nasal bleeding in the last 3 months?		
Are you pregnant?		
Are you allergic or sensitive to silicone?		
Do you have any underlying medical condition that would prevent your ability to perform treatment?		
Are you immunosuppressed or on immunosuppressant medications, such as prednisone or chemotherapy agents?		

**Baseline medical history and exam****SinuSonic Study**

PI: [name]

Subject ID#: \_\_\_\_\_ Subjects Initials: \_\_\_\_\_

**DEMOGRAPHIC AND CLINICAL VARIABLES (If not previously collected):****Age at enrollment (years):** \_\_\_\_\_

--	--

**Gender:**      Male      Female**What is/was your profession (current/retired)?** \_\_\_\_\_

Do you have significant daily contact with young children (age under 12 years)? Yes / No

Do you fly frequently, ie more than twice per month? Yes / No

**LANGUAGE, ETHNICITY, RACE, MARITAL STATUS****Please mark one of the following categories which describes your native language:**

American English  
 Other: please specify \_\_\_\_\_

**Please mark one of the following categories which describes your ethnicity:**

Not Hispanic or Latino  
 Hispanic or Latino

**Please mark one or more of the following categories which describes your race:**

American Indian or Alaska Native  
 Asian  
 Black or African American  
 Native Hawaiian or Other Pacific Islander  
 White  
 Other

**SMOKING HISTORY****1. Do you currently smoke tobacco products?****Yes    No    (If No please go to question 2)**

How many tobacco products do you use in a day?	Singles	Packs
Have you been tested for COVID19?	Yes	No
If yes, were you positive?	Yes	No

### CURRENT MEDICATION USAGE

 Nasal steroid sprays (Flonase, Nasonex, etc)	 Yes	 No
 Nasal antihistamine spray (Astelin, etc)	 Yes	 No
 Oral antihistamines (Allegra, Claritin, Benedryl, etc)	 Yes	 No
 Oral decongestant (Sudafed, etc)	 Yes	 No
 Mucolytic (Mucinex, etc)	 Yes	 No
 Luekotriene (Singulair, etc)	 Yes	 No

### COMORBID MEDICAL CONDITIONS: Check box and provide details if present

 Obstructive Sleep Apnea:	 Currently being treated	 History / No current treatment
 Allergic rhinitis:		
 Previous allergy testing (blood test or skin prick):	 Yes	 No
 Immunotherapy shots for allergies:	 Yes	 No
 Non-allergic rhinitis	 Yes	 No
 Asthma	 Yes	 No
 Chronic rhinosinusitis	 Yes	 No
 Nasal polyps	 Yes	 No
 Prior ear/sinus surgery	 Yes	 No
 Migraine headache history:	 Resolved/past diagnosis	 Present/medicated
<hr/>		
 Height (ft/in):		
 Weight (lbs):		

## **DAILY URI SYMPTOM SCORE**

**To be completed each evening**

PLEASE RATE HOW BOthersome YOUR SYMPTOMS  
HAVE BEEN OVER THE PAST DAY

	Not at all	Mild	Moderate	Severe
Lost sense of smell/taste	0	1	2	3
Sneezing	0	1	2	3
Runny nose or thick nasal discharge	0	1	2	3
Nasal obstruction or congestion	0	1	2	3
Sore throat	0	1	2	3
Cough	0	1	2	3
Headache	0	1	2	3
Malaise (feeling unwell or exhausted)	0	1	2	3
Chilliness	0	1	2	3
TOTAL SYMPTOM SCORE (TSS) of last 8 items				

Do you feel like you have a cold today? Yes/No

How many times did you use Sinusonic in the last 24 hours?

**Week 8 patient satisfaction/safety**

How much pain did you experience using device?    None    Mild    Moderate    Severe

Bleeding after using device?    None    Mild    Moderate    Severe

Would you use device again?    Yes    No

Would you recommend device to others?    Yes    No
